8.1.1 Dose Discontinuation Criteria for Cabiralizumab and Nivolumab

Discontinuation rules may be different for monotherapy and combination therapy and not all rules will apply to both arms of the study. For comprehensive discontinuation rules, refer to [Appendix 6](#) (monotherapy) and [Appendix 7](#) (combination therapy) or [Appendix 8](#) (laboratory abnormalities).

Treatment of cabiralizumab in monotherapy or cabiralizumab in combination with nivolumab should be discontinued in the following cases unless otherwise specified:

- Any Grade 3 or higher uveitis *or* any Grade 2 drug-related uveitis, eye pain, or blurred vision that does not respond to topical therapy and does not improve to Grade 1 within the second re-treatment period *or* that requires systemic treatment

- Any Grade 3 or higher infusion-related reactions and hypersensitivity requiring discontinuation. Any re-initiation of therapy in this circumstance would require consultation with the Sponsor's Medical Monitor or designee.
- Any Grade 3 non-skin, drug-related AE lasting >7 days, including drug-related uveitis, pneumonitis, hypoxia, bronchospasm, and endocrinopathies with the following exceptions:
 - Grade 3 drug-related endocrinopathies adequately controlled with only physiologic hormone replacement do not require discontinuation
 - Grade 3 drug-related laboratory abnormalities do not require treatment discontinuation except:
 - Grade 3 drug-related thrombocytopenia >7 days or associated with Grade ≥ 2 bleeding requires discontinuation
- Any drug-related liver function test (LFT) abnormality that meets any one of the following criteria requires discontinuation:
 - ALT or AST $>3x$ ULN **and** total bilirubin $>2x$ ULN **or** INR $>1.5 \times$ ULN (in the absence of anticoagulation).
 - See [Appendix 6](#) and [Appendix 7](#) for guidelines and possibility of restarting therapy
 - ALT or AST $>20x$ ULN (with or without concurrent liver metastases)
 - Total bilirubin $>3x$ ULN ($>5x$ ULN with concurrent liver metastases)
- Any Grade 4 drug-related AE or laboratory abnormality, except for the following events which do not require discontinuation:
 - Grade 4 neutropenia <7 days
 - Grade 4 lymphopenia or leukopenia <7 days
 - Isolated Grade 4 amylase or lipase abnormalities that are not associated with symptoms or clinical manifestations of pancreatitis. The Sponsor's Medical Monitor or designee should be consulted for Grade 4 amylase or lipase abnormalities.

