Wherever possible, timely confirmation of initial liver-related laboratory abnormalities should occur prior to the reporting of a potential DILI event. All occurrences of potential DILIs, meeting the defined criteria, must be reported as SAEs (see [Section 9.2](#) and [Appendix 3](#) for reporting details).

Potential drug induced liver injury is defined as:

- AT (ALT or AST) elevation > 3 times upper limit of normal (ULN)
AND
- Total bilirubin > 2 times ULN, without initial findings of cholestasis (elevated serum alkaline phosphatase), or INR > 1.5 xULN (in the absence of anticoagulation)
AND
- No other immediately apparent possible causes of AT elevation and hyperbilirubinemia, including, but not limited to, viral hepatitis, pre-existing chronic or acute liver disease, or the administration of other drug(s) known to be hepatotoxic.

9.2.8 *Other Safety Considerations*

Any significant worsening noted during interim or final physical examinations, electrocardiogram, x-ray filming, any other potential safety assessment required or not required by protocol should also be recorded as a nonserious or serious AE, as appropriate, and reported accordingly.

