Grade 3–4: Diarrhea (G3): ≥7 stools per day over baseline; incontinence; IV fluids ≥24 hours; interfering with ADL; Colitis (G3): Severe abdominal pain, medical intervention indicated, peritoneal signs Grade 4: Life-threatening perforation	
 – Delay or Discontinue cabiralizumab and nivolumab therapy per protocol^b – 1 to 2 mg/kg/day methylprednisolone IV or IV equivalent^c – Add prophylactic antibiotics for opportunistic infections – Consider lower endoscopy if clinically indicated 	
If Grade 3 AE improves to Grade 1 or baseline within 28 days:
 
 – Taper steroids over at least 1 month – Resume dosing of cabiralizumab and Nivolumab 
If Grade 4:
 
 – Permanently discontinue cabiralizumab and Nivolumab – Continue steroids until Grade 1, then taper steroids over at least 1 month 
If persists >3–5 days, or recurs after improvement:
 
 – Add infliximab 5 mg/kg (if no contraindications) – Follow up until resolution – Note: Infliximab should not be used in cases of perforation or sepsis

^a If the AE requiring dose delay was due to one of the study drugs, the non-offending drug may be continued, taking into account the safety and clinical benefit to the patient

^b If the AE requiring discontinuation was due to one of the study drugs, the non-offending drug may be continued, if there is timely resolution of AE and clinical benefit is shown by patient

^c Patients on IV steroids may be switched to an equivalent dose of oral corticosteroids (e.g. prednisone) at start of tapering or earlier, once sustained clinical improvement is observed. Lower bioavailability of oral corticosteroids should be taken into account when switching to the equivalent dose of oral corticosteroids.

Renal Adverse Event Management		
Rule out noninflammatory causes. If a noninflammatory cause is identified, treat accordingly and continue nivolumab therapy.		
Grade of Creatinine Elevation (NCI CTCAE v 4.03)	Management	Follow-Up
Grade 1: Creatinine >1.0x to 1.5x baseline; >1 x ULN to 1.5x ULN	
 – Continue cabiralizumab and nivolumab therapy at the same dose level per protocol – Monitor creatinine weekly 	
If returns to baseline :
 
 – Resume routine creatinine monitoring per protocol 
If worsens:
 
 – Follow as stated below

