^a If the AE requiring dose delay was due to one of the study drugs, the non-offending drug may be continued, taking into account the safety and clinical benefit to the patient.

^b If the AE requiring discontinuation was due to one of the study drugs, the non-offending drug may be continued, if there is timely resolution of AE and clinical benefit is shown by patient.

^c Patients on IV steroids may be switched to an equivalent dose of oral corticosteroids (e.g. prednisone) at start of tapering or earlier, once sustained clinical improvement is observed. Lower bioavailability of oral corticosteroids should be taken into account when switching to the equivalent dose of oral corticosteroids.

Hepatic Adverse Event Management without Liver Metastasis

Rule out noninflammatory causes. If a noninflammatory cause is identified, treat accordingly and continue nivolumab therapy. Consider imaging for obstruction.

Grade of Liver Test Elevation	Management	Follow-Up
AST or ALT >3.0x ULN and Total bilirubin >2x ULN or INR > 1.5	
 – Discontinue cabiralizumab and nivolumab per protocol – Start steroids 	
 – Continue LFT monitoring per protocol until resolution. – Continue monitoring for and other associated clinical signs or symptoms – Contact the Medical Monitor – Evaluate for non drug related causes of the laboratory abnormalities (e.g. obstruction, viral infection, Gilbert's disease, etc) – Under selected circumstances (e.g alternative etiology is identified), patient may receive additional therapy only after consultation and agreement between the Sponsor/MM and the investigator if receiving additional treatment with cabiralizumab and nivolumab is in the best interest of the patient (e.g if the subject has demonstrated a response to therapy)

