AST or ALT > 12 to ≤ 20 xULN and Total bilirubin ≤ 2 xULN or Isolated total bilirubin > 2 to ≤ 3 xULN	
 – Delay cabiralizumab and nivolumab therapy per protocol^a – Increase frequency of monitoring of (including but not limited to) AST, ALT, bilirubin, alkaline phosphatase and INR (every 48-72 hours or more frequently, as clinically indicated) – If there is a 2-fold ALT increase compared to the previous measurement, start steroids immediately – Consider steroid treatment on any total bilirubin increase of over 2.0x ULN – If there is a concurrent increase of alkaline phosphatase along with ALT, start steroids immediately 	
If AST/ALT return to ≤ 12 xULN within ≤ 7 days:
 
 – Resume routine monitoring – Resume cabiralizumab and nivolumab therapy at same dose level per protocol 
If elevations persist and remain at the same level > 7 days but ≤ 28 days:
 
 – Start steroids immediately and discontinue further dosing – Continue monitoring and consider dosing the subject with nivolumab therapy at the same dose level. – Consider tapering steroids over at least 1 month 
If elevations persist at the same level > 28 days or worsen:
 
 – Discontinue cabiralizumab and nivolumab therapy per protocol – 0.5-1 mg/kg/day methylprednisolone or oral equivalent and when LFT returns to Grade 1 or baseline, taper steroids over at least 1 month – Consider prophylactic antibiotics for opportunistic infections – Discuss with Medical Monitor

Hepatic Adverse Event Management without Liver Metastasis

Rule out noninflammatory causes. If a noninflammatory cause is identified, treat accordingly and continue nivolumab therapy. Consider imaging for obstruction.

Grade of Liver Test Elevation	Management	Follow-Up
	
 Monitor for other clinical symptoms (fatigue, nausea, vomiting, abdominal pain, fever, rash, and/or eosinophilia) 	

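### In both Appendix 7 hepatic tables, the header continues nivolumab for a noninflammatory cause while the first row stops both drugs; the seven headers with this sentence do not mention cabiralizumab

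*Protocol*

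**What the plan says.** Appendix 7 of the protocol governs adverse event management in cohorts C1 and C2. It has two hepatic tables, one for subjects without and one for subjects with liver metastasis. Both open with a header that asks sites to rule out noninflammatory causes and then says "If a noninflammatory cause is identified, treat accordingly and continue nivolumab therapy. Consider imaging for obstruction".

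The first row of each table applies when AST or ALT exceeds 3x ULN together with total bilirubin above 2x ULN or INR above 1.5. In the table without liver metastasis, the management cell says "Discontinue cabiralizumab and nivolumab per protocol" and "Start steroids"; the table with liver metastasis gives the same two instructions. The follow-up cell asks for evaluation of causes unrelated to drug, with obstruction, viral infection and Gilbert's disease as examples. In selected circumstances, such as an alternative etiology, it says that the "patient may receive additional therapy only after consultation and agreement between the Sponsor/MM and the investigator".

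Section 8.1.1 introduces its hepatic criteria with "Any drug-related liver function test (LFT) abnormality that meets any one of the following criteria requires discontinuation". It also names Appendix 7 as the place for the comprehensive discontinuation rules in combination therapy. For the criterion that matches the first row, it sends sites to Appendices 6 and 7 on the possibility of restarting.

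The header sentence "If a noninflammatory cause is identified, treat accordingly and continue nivolumab therapy" also stands above the gastrointestinal, renal, pulmonary, endocrine and skin tables.

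**The concern.** A header and a row of the same table give opposite actions on nivolumab for the same patient. Whether that patient stays on nivolumab, and whether steroids start before the cause has been evaluated, depends on which line the site follows. That is first a matter of patient safety.

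It also reaches a secondary endpoint. Adverse events leading to discontinuation are part of the C1 and C2 safety assessment. SAP Section 7.1.1 identifies them by the CRF action taken, and its AE tables are regardless of causality unless otherwise specified. SAP Section 7.6.3 summarises them by cohort. A hepatic event with a non-drug cause can therefore count or not count in the all-cause table according to the line followed rather than the patient's course.

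The header also leaves cabiralizumab open: it says what happens to nivolumab and is silent on the other study drug.

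**Working it through.** The plan states no figure on this point, so the check sets the texts side by side.

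**Step 1. One case, three texts.** Take a C1 subject whose liver tests meet the first row and whose cause proves to be biliary obstruction. The header itself links obstruction to its search for noninflammatory causes, and the row names obstruction among the causes to evaluate, so both texts cover this subject.

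| Text | Nivolumab | Cabiralizumab | Steroids |
|---|---|---|---|
| Hepatic header | Continue | Not mentioned | Not mentioned |
| First row | Discontinue; further dosing only by agreement | Discontinue; further dosing only by agreement | Start, no condition stated |
| Section 8.1.1 | Discontinuation criterion covers drug-related abnormalities only | Same | Not mentioned |

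**Step 2. Is the header a gate?** If the rows applied only after noninflammatory causes had been excluded, there would be no conflict. The first row rules this out, because it deals with the case where another etiology is identified and attaches its own condition to it.

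**Step 3. Do the footnotes release a drug?** Footnotes a and b let the drug not responsible continue when the event is due to one of the study drugs. Neither is attached to the first row, and neither addresses an event due to no study drug.

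**Step 4. Does Section 8.1.1 settle it?** It is narrower than the row in scope (drug-related only) but defers to Appendix 7 for the comprehensive rules and for restarting. The section points to the table, and the row points back with the words *per protocol*.

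**Step 5. How far does the clash reach?** Each hepatic table has four rows, so 2 x 4 = 8. The combination of stopping both drugs, starting steroids and requiring agreement despite another etiology occurs only in the first row of each: 2 of 8. Of the others, the >5 to ≤12x row continues both drugs if there are no clinical signs of significant muscle or hepatic damage. The >12 to ≤20x row delays, with footnote a. The >20x row discontinues, with footnote b, and steroids are only to be considered.

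**Step 6. Silence on cabiralizumab.** Appendix 7 has 11 tables. Seven carry the header sentence: gastrointestinal, renal, pulmonary, two hepatic, endocrine and skin. Headers among these that mention cabiralizumab: 0 of 7. The rows beneath them manage both drugs.

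**Step 7. Weight of one subject.** 1/6 = 16.7% of a 6-subject cohort; 1/12 = 8.3% of a cohort expanded to 12. This is the weight of any single subject, not an estimate of how often the conflict arises.

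**The case against.** The strongest defence is that the row discontinues *per protocol*, and the protocol text is Section 8.1.1, which is limited to drug-related abnormalities. Section 7.4.2 likewise speaks of resuming when a drug-related event resolves. On that reading the limit is carried into the row by reference, and the row's follow-up cell is the specific restart rule that overrides a generic header. This is a reasonable reading, but the documents do not state it. Section 8.1.1 treats Appendix 7 as the fuller source, and the row stops treatment on laboratory values before the cause has been evaluated.

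A second defence is that sites are not left alone: first-row cases require contact with the Medical Monitor, and Section 9 requires immediate safety concerns to be discussed with the sponsor. That stands and lowers the risk. It does not tell either party which line governs.

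Some stronger readings are tempting and are not supported:

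- A reader might infer that the conflict arises for every non-drug hepatic event meeting the first row. The header says *noninflammatory* and the row says *non drug related*; these overlap for obstruction but are not the same term, and viral infection, one of the row's examples, shows that they need not coincide.
- A reader might see a second contradiction in the >12 to ≤20x row, where "If there is a concurrent increase of alkaline phosphatase along with ALT, start steroids immediately" seems to clash with the cholestasis wording in Section 9.2.7. Section 9.2.7 defines which events are reported as potential DILI; it is not a management rule. Its cholestasis qualifier attaches to bilirubin above 2x ULN, whereas the transaminase limb of that row requires bilirubin at or below 2x ULN.
- A reader might extend the clash to all of Appendix 7. In the other five tables with the header, no row addresses an alternative etiology, so only the silence on cabiralizumab applies. The neurological, periorbital edema, infusion reaction and uveitis tables have no such header.

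**Conclusion.** The point holds within stated limits. In both hepatic tables, the header and the first row give opposite instructions on nivolumab for a noninflammatory cause, such as obstruction, that meets the row. Section 8.1.1 adds a drug-related limit that the row does not state, and does not resolve the conflict. Separately, none of the seven headers says what applies to cabiralizumab.

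The conclusion rests on the text alone and on treating obstruction as a noninflammatory cause, as the header's own wording implies. How often the case would occur cannot be sized from the documents. A reader might infer a raised frequency because pancreatic cancer patients may enter, but the only relevant text is an albumin criterion. A reader might also infer an effect of steroids on the activity results; the documents give no basis for one, and BOR and DOR are only listed. That steroids would continue after another cause is found is likewise an inference: the row starts them and is silent on what follows.

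The change is worth making because the contradiction concerns dosing and steroid exposure within one table.

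**What to change.** Reconcile three texts: the headers of the two hepatic tables, the first row of each, and the hepatic criteria in Section 8.1.1. The reconciled wording should state:

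- whether the header or the row governs when a noninflammatory cause is identified;
- whether the first row applies to abnormalities that are not drug-related;
- how the instruction to start steroids relates to the evaluation of cause.

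In the seven headers that carry the nivolumab sentence, state what applies to cabiralizumab. The four Appendix 7 tables without that header need no change on this account.

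The sponsor's clinical team decides which instruction stands; this review does not propose one. The cost is wording in seven headers, two rows and, if needed, one section, with no added procedures or data collection.

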Male CrCl = $\frac{(140 - \text{age in years}) \times \text{weight in kg} \times 1.0}{72 \times \text{serum creatinine in mg/ dL}}$
- v) PT/INR \leq 1.5 x ULN and PTT (aPTT) \leq 1.5 x ULN
- vi) AST \leq 3.0 x ULN
- vii) ALT \leq 3.0 x ULN
- viii) Total Bilirubin \leq 1.5 x ULN (except subjects with Gilbert Syndrome who must have a total bilirubin level of < 3.0 x ULN)

3) Age and Reproductive Status

- a) Males and Females, \geq ages 20
- b) Women of childbearing potential (WOCBP) must have a negative serum or urine pregnancy test (minimum sensitivity 25 IU/L or equivalent units of HCG) within 1 day prior to the start of study treatment.
- c) Women must not be breastfeeding (Even if breastfeeding is suspended, participation in the study is not allowed)
- d) Women of childbearing potential (WOCBP) must agree to follow instructions for method(s) of contraception for the duration of treatment with study treatment(s) and for a total of 5 months post-treatment completion.
- e) Males who are sexually active with WOCBP must agree to follow instructions for method(s) of contraception ([Appendix 4](#)) for the duration of treatment with study treatment(s) and for a total of 7 months post-treatment completion. In addition, male participants must be willing to refrain from sperm donation during this time.
- f) Azoospermic males are exempt from contraceptive requirements. WOCBP who are continuously not heterosexually active are also exempt from contraceptive requirements, and still must undergo pregnancy testing as described in this section.

Investigators shall counsel WOCBP, and male participants who are sexually active with WOCBP, on the importance of pregnancy prevention and the implications of an unexpected pregnancy. Investigators shall advise on the use of highly effective methods of contraception ([Appendix 4](#)) which have a failure rate of $< 1\%$ when used consistently and correctly.

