APPENDIX 6 AE MANAGEMENT FOR CABIRALIZUMAB MONOTHERAPY COHORTS

Hepatic Adverse Event Management without Liver Metastasis		
Grade of Liver Test Elevation	Management	Follow-Up
AST or ALT $>3.0 \times \text{ULN}$ and Total bilirubin $>2 \times \text{ULN}$ or INR > 1.5	
 – Discontinue cabiralizumab therapy per protocol 	
 – Continue LFT monitoring per protocol until resolution. – Continue monitoring for and other associated clinical signs or symptoms – Contact the Medical Monitor – Evaluate for non-drug related causes of the laboratory abnormalities (e.g. obstruction, viral infection, Gilbert's disease, etc) – Under selected circumstances (e.g alternative etiology is identified), patient may receive additional therapy only after consultation and agreement between the Sponsor/MM and the investigator if receiving additional treatment with cabiralizumab is in the best interest of the patient (e.g if the subject has demonstrated a response to therapy)
AST or ALT > 5 to $\leq 12 \times \text{ULN}$ and Total bilirubin $\leq 2 \times \text{ULN}$	
 – Continue cabiralizumab therapy if there are no clinical signs of significant muscle or hepatic damage – Increase frequency of monitoring of AST, ALT, bilirubin, alkaline phosphatase and INR (every 48-72 hours or more frequently, as clinically indicated) – Monitor for other clinical symptoms (fatigue, nausea, vomiting, abdominal pain, fever, rash, and/or eosinophilia) 	
 – Contact the Medical Monitor if there are clinical signs of muscle or hepatic injury or other clinical symptoms – Contact the Medical Monitor if there is a concurrent increase of bilirubin, AST, ALT, or alkaline phosphatase from baseline. – Notify the Medical Monitor if there is an AST increase $> 5 \times \text{ULN}$ – Frequency of retesting can decrease to once a week or less if abnormalities stabilize or the trial drug has been discontinued and the subject is asymptomatic – Consider gastroenterology or hepatology referral

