AST or ALT >12 to $\leq 20 \times \text{ULN}$ and Total bilirubin $\leq 2 \times \text{ULN}$ or Isolated total bilirubin > 2 to $\leq 3 \times \text{ULN}$	
 – Delay cabiralizumab therapy per protocol – Increase frequency of monitoring (including but not limited to) of AST, ALT, bilirubin, alkaline phosphatase and INR (every 48-72 hours or more frequently, as clinically indicated) – Monitor for other clinical symptoms (fatigue, nausea, vomiting, abdominal pain, fever, rash, and/or eosinophilia) – Consider imaging to rule out obstruction 	
If AST and ALT $\leq 12 \times \text{ULN}$ for ≤ 28 days:
 
 – Resume routine monitoring – Resume cabiralizumab therapy at same dose level per protocol 
If elevations persist at same level for > 28 days or worsen:
 
 – Discontinue cabiralizumab therapy per protocol – Discuss with Medical Monitor
AST or ALT $> 20 \times \text{ULN}$ or Total bilirubin $>3 \times \text{ULN}$	
 – Discontinue cabiralizumab therapy 	
 – Continue LFT monitoring per protocol until resolution – Continue monitoring for and other associated clinical signs or symptoms

Hepatic Adverse Event Management with Liver Metastasis		
Grade of Liver Test Elevation	Management	Follow-Up
AST or ALT $>3.0 \times \text{ULN}$ and Total bilirubin $>2 \times \text{ULN}$ or INR > 1.5	
 – Discontinue cabiralizumab therapy per protocol 	
 – Continue LFT monitoring per protocol until resolution. – Continue monitoring for and other associated clinical signs or symptoms – Contact the Medical Monitor – Evaluate for non drug related causes of the laboratory abnormalities (e.g. obstruction, viral infection, Gilbert's disease, etc) – Under selected circumstances (e.g alternative etiology is identified), patient may receive additional therapy only after consultation and agreement between the Sponsor/MM and the investigator if receiving additional treatment with cabiralizumab is in the best interest of the patient (e.g if the subject has demonstrated a response to therapy)

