AST or ALT >3.0x ULN and Total bilirubin >2x ULN or INR > 1.5	
 – Discontinue cabiralizumab and nivolumab therapy per protocol – Start steroids 	
 – Continue LFT monitoring per protocol until resolution. – Continue monitoring for and other associated clinical signs or symptoms – Contact the Medical Monitor – Evaluate for non drug related causes of the laboratory abnormalities (e.g. obstruction, viral infection, Gilbert's disease, etc) – Under selected circumstances (e.g alternative etiology is identified), patient may receive additional therapy only after consultation and agreement between the Sponsor/MM and the investigator if receiving additional treatment with cabiralizumab and nivolumab is in the best interest of the patient (e.g if the subject has demonstrated a response to therapy)
AST or ALT > 5 to \leq 12 xULN and Total bilirubin \leq 2 xULN	
 – Continue cabiralizumab and nivolumab therapy if there are no clinical signs of significant muscle or hepatic damage – Increase frequency of monitoring of AST, ALT, bilirubin, alkaline phosphatase and INR (every 48-72 hours or more frequently, as clinically indicated) – Monitor for other clinical symptoms (fatigue, nausea, vomiting, abdominal pain, fever, rash, and/or eosinophilia) 	
 – Contact the Medical Monitor if there are clinical signs of muscle or hepatic injury or other clinical symptoms – Contact the Medical Monitor if there is a concurrent increase of bilirubin, AST, ALT, or alkaline phosphatase – Notify the Medical Monitor if there is an AST or ALT increase > 5 xULN – Frequency of retesting can decrease to once a week or less if abnormalities stabilize or the trial drug has been discontinued and the subject is asymptomatic. – Consider gastroenterology or hepatology referral

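### All four hepatic tables stop treatment at a bare INR above 1.5, while 8.1.1 requires INR above 1.5 x ULN without anticoagulation; their isolated-bilirubin delay rows also lack a bilirubin resume level

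*Protocol*

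**What the plan says.** Appendix 6 (monotherapy) and Appendix 7 (combination) each contain two hepatic tables, one without and one with liver metastasis.

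**Stop row.** The first row of the Appendix 7 table without liver metastasis is "AST or ALT >3.0x ULN and Total bilirubin >2x ULN or INR > 1.5". The Appendix 7 table with liver metastasis repeats "Total bilirubin >2x ULN or INR > 1.5", and both Appendix 6 tables use the same INR cut. The instruction is to discontinue; in Appendix 7 it is also to start steroids. Section 8.1.1 has the corresponding stop with "INR $>1.5 \times$ ULN (in the absence of anticoagulation". Section 9.2.7, which defines potential drug-induced liver injury for reporting, has "INR > 1.5 xULN (in the absence of anticoagulation". The entry limit in 6.1 is also a multiple of the ULN: "PT/INR \leq 1.5 x ULN". On precedence, 8.1.1 tells sites: "For comprehensive discontinuation rules, refer to" the appendices.

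**Delay row.** Each table delays dosing for isolated total bilirubin: above 2 and up to 3 x ULN without liver metastasis, above 3 and up to 5 x ULN with it. In Appendix 6 the resume condition begins "If AST and ALT $\leq 12 \times \text{ULN}$ for" and continues with a limit of 28 days. In Appendix 7 it is AST/ALT coming back to 12 x ULN or less within 7 days. Section 7.4.2 ties resumption to resolution of the drug-related event as these tables describe it.

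**The concern.** A stopping rule should give one answer for one set of laboratory results. Here a site reading the tables and a site reading 8.1.1 can reach opposite decisions on the same subject, and in the combination cohorts the table reading adds steroids.

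The choice also reaches the endpoints. SAP 7.1.1 identifies adverse events leading to discontinuation from the recorded action taken. These events belong to the primary endpoint in M1 and M2 and to a secondary endpoint in C1 and C2.

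The bilirubin rows raise a related problem. A hold triggered by one analyte has a release condition written only for two others, so the table does not say when a subject held for bilirubin may be dosed again.

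**Working it through.** No figure in the plan needs reproducing. The check sets the rules side by side and adds simple arithmetic for the INR band.

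**INR stop rule**

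| Source | INR cut | Anticoagulation exception |
|---|---|---|
| Appendix 6, both hepatic tables | above 1.5 | none |
| Appendix 7, both hepatic tables | above 1.5 | none |
| Section 8.1.1 | above 1.5 x ULN | yes |
| Section 9.2.7 (reporting) | above 1.5 x ULN | yes |

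Four of four tables carry the bare cut. If bilirubin is above 2 x ULN, both rules stop whatever the INR. Take instead AST or ALT above 3 x ULN and bilirubin at or below 2 x ULN, with no anticoagulation. The rules then disagree when 1.5 < INR <= 1.5 x ULN. The documents give no INR ULN, so it is assumed over a range:

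- ULN 1.0: 1.5 x 1.0 = 1.50, no band.
- ULN 1.1: 1.5 x 1.1 = 1.65, band above 1.50 to 1.65.
- ULN 1.2: 1.5 x 1.2 = 1.80, band above 1.50 to 1.80.

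Example at ULN 1.1: INR 1.6 is 1.6 / 1.1 = 1.45 x ULN, which meets the entry limit. If ALT then rises to 3.1 x ULN with bilirubin at or below 2 x ULN, the tables stop treatment and 8.1.1 does not. Without the INR trigger, that ALT falls in no table row until it exceeds 5 x ULN.

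Under anticoagulation, 8.1.1 does not count the INR at all, so with the same transaminase and bilirubin values the rules disagree at any INR above 1.5.

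**Isolated-bilirubin delay rows**

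Rows with a bilirubin resume level: 0 of 4. Take a subject whose AST and ALT are normal throughout.

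- Appendix 6, no liver metastasis, bilirubin 2.5 x ULN: AST and ALT are already at or below 12 x ULN, so the resume condition is met while the same row orders a delay.
- Appendix 7, no liver metastasis, bilirubin falling from 2.9 to 2.1 x ULN by day 10: AST/ALT have nothing to return from, and the elevation is neither at the same level nor worse. No branch applies. None applies if bilirubin becomes fully normal either.

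Elsewhere the protocol releases a hold on the parameter that caused it: creatinine at Grade 1 or baseline (Appendix 7), CK or LDH at 15 x ULN or less (Appendix 8), periorbital edema at Grade 1 or baseline (Appendix 6). That pattern suggests an omission here.

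**The case against.** The strongest reply on INR is that the two texts can be read together. The table rows say to discontinue according to the protocol, and 8.1.1 yields where something else is specified. This does not settle precedence, because each text defers to the other.

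Three limits do stand. The tables err towards an earlier stop. The stop is reversible: "patient may receive additional therapy only after consultation and agreement between the Sponsor/MM and the investigator". And the anticoagulated group is narrowed at entry, because the INR limit in 6.1 has no anticoagulation exception and 6.2 excludes coagulopathy. What remains is mainly a rise in INR after entry. The section between 7.6 and 7.8 is blacked out, so the frequency of on-study anticoagulation cannot be judged. Both Appendix 7 hepatic tables also let nivolumab continue when a noninflammatory cause is found, which might cover an anticoagulant effect, but only for nivolumab and only in that appendix.

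On bilirubin, a reader might infer that Appendix 6 permits redosing on the first day of a hold. The documents do not support that: while bilirubin is in the band the row's instruction is to delay, and 7.4.2 requires the drug-related event to have resolved. A reader might also infer that Appendix 7 forces steroids and ends dosing after 7 days for every such subject. That branch needs the elevation to stay at the same level, and it leaves nivolumab open for consideration. The intended reading is fairly evident, but it is not written down.

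**Conclusion.** The INR rule is wrong as written: four tables conflict with 8.1.1 on a decision threshold, and nothing in the text says which prevails. The numeric band depends on the assumed ULN and vanishes at 1.0; the missing anticoagulation exception remains at any ULN. The bilirubin gap is real but secondary. It is a missing release criterion, contradictory in Appendix 6 and absent in Appendix 7 for a subject who recovers.

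The documents do not say how many subjects would be affected, so no rate is claimed. Sample size and error rates are untouched, and the endpoint effect is limited to descriptive counts.

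Two stronger readings should be set aside. Because the row joins its conditions without brackets, a reader might infer that INR above 1.5 alone stops treatment; the natural reading, and the grouping in 9.2.7, also require raised AST or ALT. A reader might also infer that a subject admitted with Gilbert syndrome and a stable bilirubin below 3 x ULN would be held at once. Appendix 3 defines an adverse event as new or worsening, and 7.4.2 speaks of drug-related events, so such a value can be read as outside the tables.

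**What to change.** 1. In the first row of all four hepatic tables, write: AST or ALT >3 x ULN AND (total bilirubin >2 x ULN OR INR >1.5 x ULN in the absence of anticoagulation). Use the same bracketing in 8.1.1 so that the two texts match.
2. In each isolated-bilirubin delay row, add a bilirubin resume criterion at the row's lower bound: total bilirubin at or below 2 x ULN without liver metastasis, at or below 3 x ULN with it, or return to baseline. The sponsor's medical team should confirm the level.

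The cost is wording in four tables and one line of 8.1.1. Bilirubin and PT/INR are already in the laboratory panel of 9.4.4, so no test is added.
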